9 QUALITY CONTROL AND QUALITY ASSURANCE

- Data on patient-reported outcomes will be collected using standardized measures that have been validated in other samples.
- On a monthly basis, the project coordinator will print frequency data from surveys and examine for unexpected results or patterns of missingness. Any issues will be resolved with the PI.
- If there are any discrepant results in a participant's record, they may be contacted by phone for further clarification.
- The PI and the project coordinator will ensure all survey data are backed-up on UM's secure network, and will also ensure that data are password-protected and only accessible to the research team.
- The project coordinator will ensure that all participants are accounted for in tracking database.
- Each month, participant IDs will randomly be selected to ensure that consents have been obtained.

10 STATISTICAL CONSIDERATIONS

- Outcomes in primary analysis
 - Number of doses in the discharge opioid prescription
 - Proportion of patients in which the number of doses in the discharge opioid prescription equals the number of doses in the new default settings
 - Proportion of patients prescribed opioids at discharge
 - Proportion of patients prescribed opioids at discharge who had at least one opioid prescription refill from UM during the two weeks after surgery
 - Proportion of patients who saw a UM provider in an office due to pain during the two weeks after surgery

- Proportion of patients with at least one emergency department visit or hospitalization at UM for pain during the two weeks after surgery
- Additional outcomes in secondary analysis (based on data from the final post-operative day 14 survey)
 - Overall satisfaction with pain control during the two weeks after surgery (scale of 1-10)
 - Proportion of patients who reported that their pain was well-controlled
 - Proportion of patients whose overall pain control was rated as much worse or worse than expected
 - Proportion of patients whose pain has resolved by day 14 after surgery
 - Pain score over the past 7 days at its worst (scale of 0-10)
 - Pain score over the past 7 days on average (scale of 0-10)
 - Number of opioid doses taken during the two weeks after surgery
 - Proportion of patients with leftover doses of opioids
 - Proportion of patients with leftover doses who disposed of them
 - Proportion of patients who misused opioids belonging to others at least once during the two weeks after surgery
 - Proportion of patients who misused their own opioids at least once during the two weeks after surgery
 - PHQ-8 score (depression)
 - Score on PROMIS Pediatric Anxiety – Short Form 8a
 - Score on PROMIS Sleep Disturbance – Short Form 8a
 - Proportion of patients who saw their primary care provider (or a colleague) in the office due to poorly controlled pain at least once during the two weeks after surgery
 - Proportion of patients who visited an urgent care center due to poorly controlled pain at least once during the two weeks after surgery
 - Proportion of patients who visited a retail clinic due to poorly controlled pain at least once during the two weeks after surgery
 - Proportion of patients who went to an emergency department and/or were hospitalized due to poorly controlled pain at least once during the two weeks after surgery
- Data from the daily surveys will be used to assess whether daily opioid consumption reports matches the consumption reported on the final post-operative day 14, and will also be analyzed in a separate study assessing the trajectory of pain and opioid use after tonsillectomy.
- We will fit linear or logistic regression models assessing outcomes as a function of an indicator of post-intervention status, an indicator of treatment group status, and its interaction, controlling for covariates such as demographics (e.g., age, sex) and baseline co-morbidities (e.g., depression, anxiety). We will graphically and statistically assess the comparability of pre-intervention monthly trends in outcomes between the treatment and control groups.

- We hypothesize that there will be no change in outcomes in the control group (i.e., that the post-intervention trend in outcomes in the control group will be an extension of the pre-intervention trend in outcomes). In contrast, we hypothesize that the number of doses and opioid consumption will drop in the treatment group after the intervention; that the proportion of patients with prescriptions concordant with the new defaults will increase after the intervention; and that there will be no change in balancing measures such as pain control or depression.
- Sensitivity analyses
 - Statistical modeling: we will explore whether results change when replacing the indicator of treatment group status with a vector of fixed effects for the prescribing clinician, and will explore the feasibility of using an interrupted time series approach instead of a difference-in-differences approach.
 - We will determine whether any otolaryngology residents wrote opioid prescriptions for both a pediatric otolaryngology and general otolaryngology patients in the post-intervention period, and exclude data from any such residents from the analysis
 - We will exclude opioid prescriptions written for patients of the chief of pediatric otolaryngology, who will be involved in setting the new defaults
- Subgroup analysis will occur by age group (ages 12-17 years vs 18 and older), gender, payer type (private/public), and baseline co-morbidities (e.g., depression and anxiety).
- We will separately analyze data from pediatric otolaryngology patients undergoing surgery outside of Mott and general otolaryngology patients undergoing surgery at Mott to assess for any spillover effects.
- Sample size: Based on historical UM data, we estimate that there will be 113 patients in the treatment group and 85 in the control group for the primary analysis (total 198). If 65% consent to complete the surveys, then there will be 74 and 55 patients in the treatment and control groups for the secondary analysis, respectively (total 129).

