- Daily surveys: At 12:01 am on post-operative days 1 through 13, patients will be e-mailed a daily link to complete a 1-minute online Qualtrics survey in which pain and opioid consumption over the prior 24 hours will be assessed. The post-operative day 7 survey will be similar except that it will include additional questions assessing pain over the prior 7 days. Patients who cannot receive e-mail links will not be sent daily surveys. E-mail or telephone follow-up will not occur for the daily surveys on post-operative days 1-13.
 - Final survey: on post-operative day 14, patients will be e-mailed a link to complete a 10-15-minute online Qualtrics survey assessing pain control, opioid use, opioid disposal, opioid misuse, acetaminophen/ibuprofen use, depression, anxiety, sleep, and health care utilization during the 14 days after surgery, including refills and visits to the emergency department or primary care for pain. Patients who cannot receive e-mail links will be called and the survey will be administered over the phone. Patients may be contacted via e-mail or by phone to remind them to complete surveys. If patients are contacted by phone, they will be given the option to complete the survey over the phone.
 - DataDirect and MiChart will be queried to determine opioid use prior to the day of surgery based on the admission history and physical, patient demographics, the dosing parameters of post-operative opioid prescriptions, the number of return visits for pain at the University of Michigan in the 14 days after surgery, and the number of opioid refills in the 14 days after surgery.
- Timeline
 - The pre-intervention period will start on October 1, 2019 and end September 30, 2020; the months of April and May 2020 will be excluded as elective surgeries were scaled down owing to the COVID-19 pandemic. The intervention will be implemented on October 1, 2020. The post-intervention period will start October 1, 2020 and end on July 31, 2021.
 - Nature of intervention
 - Currently, pediatric otolaryngology attendings and their residents use a MiChart tonsillectomy orderset with three options: patients < 12 years, patients ≥12 years, and M-POP. Under the orderset for patients ≥12 years, the default is currently 30 doses, consistent with the current departmental prescribing standard (see MiChart screenshot below).
 - During the pre-intervention period, no changes will be made to the default number of doses or any other dosing parameter.

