actions taken by the project staff, planned follow up, whether the event appears related to the intervention, and whether the participant will continue in the study.

- Managing Participant Distress
 - Participants will be made aware of their right to refuse to answer any questions that make them uncomfortable or that they do not wish to answer, and they will be informed of their right to withdraw from the study at any time without penalty. This message will be conveyed during the informed consent process. All participants will have direct access to the phone number and e-mails of the study coordinator and PI.
- Managing Participant Safety
 - We will monitor pain control after surgery through the post-operative surveys described in the proposal. Of note, most post-tonsillectomy pain resolves within two weeks. We plan to conduct the post-operative surveys two weeks after surgery, so we do not anticipate that patients will still be in pain at the time the surveys are administered. However, if patients do report poor pain control, we will contact the patient's surgical team, who will follow up with the patient and prescribe opioids or bring the patient in for evaluation, as appropriate. Electronic prescribing is currently available at the University of Michigan, so patients will not necessarily have to come back in for a visit to obtain refills. In short, we do not anticipate that our intervention will worsen pain control, and have a specific plan for addressing this contingency were it to occur.

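### The records-based clinic outcome counts only office visits, so phone or video pain contacts can be missed and the comparison across the pandemic attenuated or distorted

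*Combined protocol and SAP*

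**What the plan says.** Section 10 lists, among the outcomes of the primary analysis, "Proportion of patients who saw a UM provider in an office due to pain during the two weeks after surgery". The survey-based counterpart in the secondary analysis carries the same limit: "Proportion of patients who saw their primary care provider (or a colleague) in the office due to poorly controlled pain". The other records-based harm outcomes are UM emergency visits or admissions for pain, and refills: "Proportion of patients prescribed opioids at discharge who had at least one opioid prescription refill from UM during the two weeks after surgery". The refill outcome does not depend on how the patient reached the clinician.

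Section 6 describes what will be extracted from the records in wider terms: "the number of return visits for pain at the University of Michigan in the 14 days after surgery". It names no mode of contact.

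Section 11.3 (Managing Participant Safety) says that "if patients do report poor pain control, we will contact the patient's surgical team", and notes that electronic prescribing is available, "so patients will not necessarily have to come back in for a visit to obtain refills".

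On timing, Section 6 starts the pre-intervention period on October 1, 2019 and ends it on September 30, 2020, and states that "the months of April and May 2020 will be excluded as elective surgeries were scaled down owing to the COVID-19 pandemic". It continues: "The post-intervention period will start October 1, 2020 and end on July 31, 2021". Section 10 hypothesizes no change in the balancing measures.

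**The concern.** The utilization outcomes are there to detect unintended harm. Section 1 names more refill requests and more return visits for uncontrolled pain as harms to look for. A patient who phones about pain and receives advice or a non-opioid is close to that event, yet scores no on the office, refill and emergency or admission outcomes.

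The calendar adds to this. The two periods lie unevenly around the shutdown, so the share of pain contacts that take place in an office may not be constant. The groups also differ in both service and site (Section 7 of the protocol concerns data handling; the groups are set out in Section 6), so a change in mode need not have been equal in the two. No sensitivity analysis in Section 10 addresses contact mode. The check of pre-intervention trends cannot detect a change that begins after October 2020.

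At stake is whether a finding of no change in clinic contacts can be read as reassurance.

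**Working it through.** **Figures in the plan.** Section 10 gives sample sizes but no visit rate, effect size or power. The sizes reproduce: 113 + 85 = 198; at 65% consent, 113 × 0.65 = 73.45 (stated 74), 85 × 0.65 = 55.25 (stated 55) and 198 × 0.65 = 128.7 (stated 129). Patient-reported outcomes are thus expected for about 129 patients, which leaves 198 − 129 = 69 with records-based outcomes only.

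**Months.** October 2019 to September 2020 is 12 months; less April and May 2020 it is 10. Of these, October to March (6) precede the exclusion and June to September (4) follow it. October 2020 to July 2021 is 10 months, all after it.

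**Model.** Let p be the true proportion of patients with a pain contact in a cell, and s the share of those patients whose contacts were all remote. The office-only outcome observes p(1 − s). The difference-in-differences is then

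[pT1(1 − sT1) − pT0(1 − sT0)] − [pC1(1 − sC1) − pC0(1 − sC0)],

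where T and C are the groups, and 0 and 1 the periods. If the baseline rates and pre-period remote shares are equal in the two groups, the true control rate does not change, and the post-period remote share s is common to both, a true rise r is observed as r(1 − s).

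**Assumed inputs (none is in the documents).** True contact rate 10% in every cell, except 20% in treatment-post where a rise is assumed; pre-period remote share 10% in both groups; post-period shares as shown. The pre-period terms are equal in the two groups and cancel, so each odds ratio below is the treatment-post odds over the control-post odds.

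| Truth | Remote share post, treatment / control | Observed treatment-post, control-post | Difference-in-differences | Odds ratio |
|---|---|---|---|---|
| Rise of 10 points | all modes counted | 20%, 10% | 10.0 | 0.2500/0.1111 = 2.25 |
| Rise of 10 points | 30% / 30% | 14%, 7% | 7.0 | 0.1628/0.0753 = 2.16 |
| Rise of 10 points | 50% / 50% | 10%, 5% | 5.0 | 0.1111/0.0526 = 2.11 |
| Rise of 10 points | 50% / 10% | 10%, 9% | 1.0 | 0.1111/0.0989 = 1.12 |
| Rise of 10 points | 10% / 50% | 18%, 5% | 13.0 | 0.2195/0.0526 = 4.17 |
| No change | 50% / 10% | 5%, 9% | −4.0 | 0.0526/0.0989 = 0.53 |
| No change | 10% / 50% | 9%, 5% | +4.0 | 0.0989/0.0526 = 1.88 |

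A remote share common to both groups shrinks the risk difference in proportion but barely moves the odds ratio; there the loss is mainly of events. A share that differs by group distorts both.

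**Precision.** Assume each group is split equally between periods (56.5 and 42.5 per cell) and a two-sided 5% level. With all modes counted, SE = √(0.10×0.90/56.5 + 0.20×0.80/56.5 + 2×0.10×0.90/42.5) = 0.093, and power for the 10-point rise is about 19%. Office-only counting gives about 13% at a 30% common remote share and about 10% at 50%. With every mode counted, power ranged from about 11% (5% rising to 10%) to about 54% (10% rising to 30%).

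**The case against.** A reader might infer that a real increase in uncontrolled pain would be hidden. The documents do not support that, for four reasons.

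- The visit-free route in Section 11.3 concerns refills, and UM refills are an outcome of the primary analysis whatever the mode of contact. The passage does not say that poor pain control in general is managed remotely; bringing the patient in is one of the responses it names.
- Pain control, satisfaction and pain scores are measured directly in survey completers and do not depend on visit mode.
- The control group removes a shift in mode common to both groups, apart from the proportional shrinkage of the risk difference.
- Telehealth is never mentioned. COVID-19 is cited only as the reason for fewer elective operations, so a move to remote contact is an inference and every rate above is assumed.

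It can also be said that in-person return visits are a legitimate outcome in their own right, that the difference between Sections 6 and 10 may be only loose wording, and that the outcome has low power under either definition. A spurious 4 points is only about two treated post-period patients (0.04 × 56.5 = 2.3).

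These points limit the concern but do not remove it. A remote contact without a refill, office visit, emergency visit or admission is still in no utilization outcome. The patient-reported measures are secondary and would be missing for about 69 of the 198 patients. Low power makes lost events more costly. The argument for keeping in-person visits is met by retaining them as a component.

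**Conclusion.** The point holds as a moderate weakness in an outcome definition; it is not a numerical error. As worded, the outcome can under-count pain contacts. It can attenuate the absolute size of a true rise in a measure hypothesized not to change, or bias the difference-in-differences in either direction if contact mode shifted differently between the groups.

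The shrinkage to 7 or 5 points, the 1-to-13-point range and the ±4 points under no true change illustrate the mechanism under assumed contact rates and remote shares. They are not estimates for this trial. The documents do not show that remote contacts were common, that they rose, or that they rose unequally, so neither the size nor the direction can be settled from them. Refills and patient-reported pain cover part of the gap, and a claim that harm would go undetected goes too far.

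**What to change.** Redefine the records-based outcome in Section 10 as at least one UM outpatient contact due to pain (office, video or telephone) within 14 days of surgery. Then:

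- extract it from MiChart by one rule for both groups and both periods, going back over the pre-intervention months;
- report the in-office version as a component, and tabulate contacts by mode, group and period, so that any shift in mode can be seen;
- flag contacts triggered by the study team's own notice to the surgical team (Section 11.3), since these can arise only in surveyed patients, and show the result with and without them;
- make the description of the extraction in Section 6 and the outcome in Section 10 agree.

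Leave the day-14 survey item as it is. Changing it midway would make pre- and post-intervention answers non-comparable, which is the kind of measurement change at issue here.

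The cost is a wider encounter filter in a query already planned, revised wording, and some extra chart reading to confirm that pain was the reason for telephone contacts. This assumes that MiChart records telephone and video encounters in a form that can be retrieved for both periods; the documents do not say so, and it should be confirmed first. The change will not cure the low power of this outcome.

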3 EXPECTED RISKS/BENEFITS

- There are no expected direct benefits to subjects. The expected risks for subjects are no more than minimal.
 - The most likely risk to study subjects is the time burden associated with completing the surveys.
 - There is a possible risk of breach of confidentiality, although the study team will take measures to prevent such breaches.
 - There is a possible risk of worsened pain control, although literature suggests this is unlikely. For example, an evidence-based opioid prescribing guideline was instituted for University of Michigan patients undergoing gallbladder removal in 2015 and 2016. Prior to institution of this guideline, patients received an average of 50 pills of hydrocodone/acetaminophen but only consumed 6. Institution of the guideline was associated with a 63% reduction in prescription size without increasing the need for opioid prescription refills.⁵
 - There is a possible risk that the intervention could cause depression or suicidal ideation, or that increased opioid misuse could occur. Prior studies evaluating interventions to reduce opioid prescribing for acute pain have not evaluated these outcomes, so these risks remain theoretical. However, the primary mechanism of these unintended consequences would be worsened pain control, which is unlikely given the reasons above.
- Future patients and society may benefit from the research results. The default setting intervention could be broadly applicable to other procedures and conditions, and could also be readily scalable to other institutions due to its low cost of implementation. If this intervention is successful in limiting excessive opioid prescribing to adolescents and young adults, widespread adoption could reduce the number of unused opioids available for misuse and diversion in adolescents and young adults.

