 - During the month of September 2020, opioid consumption data will be reviewed by the chief of pediatric otolaryngology. A new default

- number of doses lower than 30 will be chosen based on the level and distribution of opioid consumption.
- On October 1, 2020, the tonsillectomy orderset will be changed. The new orderset will have three options for patients ≥ 12 years: one for oxycodone solution among patients < 50 kg, one for oxycodone solution among patients ≥ 50 kg, and one for oxycodone tablets. Each of these options will auto-populate the default doses field using the new setting.
 - The new orderset will display for patients at C.S. Mott Hospital only. Thus, all patients in the treatment group (patients undergoing tonsillectomy at Mott by pediatric otolaryngology attendings) will have clinicians who are exposed to the new default settings. The tonsillectomy orderset will not be changed at University Hospital, Brighton, or Livonia. Thus, all patients in the control group (patients undergoing tonsillectomy in these locations by general otolaryngology attendings) will have clinicians who will not be exposed to the new default settings, even if they use the pediatric otolaryngology tonsillectomy orderset.

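### The disposal outcome counts only patients with leftover doses, a group the intervention is likely to change, so its estimate can move with no change in disposal behaviour

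*Combined protocol and SAP*

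**What the plan says.** Section 10 lists, among the additional outcomes of the secondary analysis, "Proportion of patients with leftover doses who disposed of them". The line before it lists "Proportion of patients with leftover doses of opioids" as an outcome in its own right. The whole list is "based on data from the final post-operative day 14 survey", so both are measured after the intervention has acted.

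Section 6 describes the intervention. Before it, "the default is currently 30 doses"; afterwards a new "number of doses lower than 30 will be chosen based on the level and distribution of opioid consumption". The change is made at C.S. Mott Hospital only.

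Section 10 models the outcomes on "an indicator of post-intervention status, an indicator of treatment group status, and its interaction", with covariates such as age, sex and baseline co-morbidities. It says nothing about an outcome whose denominator is settled after the intervention. On direction, "we hypothesize that the number of doses and opioid consumption will drop in the treatment group after the intervention". No direction is stated for leftovers or for disposal.

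Section 3 gives the wider benefit: "widespread adoption could reduce the number of unused opioids available for misuse and diversion in adolescents and young adults".

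**The concern.** Whether a patient has leftovers depends on doses supplied and doses taken. The intervention changes the first directly, and the plan expects the second to fall too. The patients who enter the disposal denominator in the treated post-period may therefore be a different selection from those in the other three cells. A difference-in-differences contrast on that denominator then mixes two things: a change in what patients do with leftovers, and a change in which patients are counted.

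The control group does not remove this, because its default stays the same and no matching change in composition is expected there. Baseline covariates remove it only so far as they account for the link between who has leftovers and who disposes.

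At stake is how one secondary result is read. A fall could be reported as worse disposal, or a rise as better disposal, when behaviour was constant. In addition, no listed outcome directly estimates the share of patients still holding undisposed opioids, which is close to the benefit named in section 3.

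**Working it through.** **The plan's own figure.** The survey sample in section 10 is the primary sample times 65% consent: 113 × 0.65 = 73.45, 85 × 0.65 = 55.25 and 198 × 0.65 = 128.7. The stated figures are 74, 55 and 129, so they reproduce to within rounding. The plan gives no leftover rate, disposal rate or power figure to reproduce.

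**Set-up (assumed).** Split treatment-group patients into three types:
- A: leftovers under either default, share a, disposal tendency dA.
- B: leftovers only under the 30-dose default, share b, disposal tendency dB.
- C: no leftovers under either default.

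Each patient's tendency is held fixed, case mix is the same in both periods, no one has leftovers only under the lower default, and the control group does not change. The difference-in-differences on the proportion scale then equals the treatment group's before-after change.

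**Formulas.**
- Conditional disposal before: (a·dA + b·dB)/(a + b). After: dA.
- Shift: [b/(a + b)] × (dA − dB).
- Undisposed leftovers among all patients before: a(1 − dA) + b(1 − dB). After: a(1 − dA).

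**Leftovers 90% to 50%** (a = 0.5, b = 0.4, so b/(a + b) = 0.444):

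| dA | dB | Conditional before | After | Shift (points) | Undisposed, all patients |
|---|---|---|---|---|---|
| 20% | 20% | (0.10 + 0.08)/0.9 = 20.0% | 20.0% | 0 | 0.40 + 0.32 = 72% to 40% |
| 20% | 40% | (0.10 + 0.16)/0.9 = 28.9% | 20.0% | −8.9 | 0.40 + 0.24 = 64% to 40% |
| 40% | 20% | (0.20 + 0.08)/0.9 = 31.1% | 40.0% | +8.9 | 0.30 + 0.32 = 62% to 30% |

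**Leftovers 90% to 70%** (a = 0.7, b = 0.2, so b/(a + b) = 0.222): the same unequal tendencies give 24.4% to 20.0% (−4.4 points) or 35.6% to 40.0% (+4.4 points).

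**What drives the shift.** It needs both that some patients leave the denominator (b above 0) and that they differ in tendency (dA not equal to dB). If either fails, the shift is zero.

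**Denominator size.** The pre-period is 12 months less April and May 2020, so 10 months; the post-period, October 2020 to July 2021, is also 10. If the 74 covers both periods and accrual is even, there are 37 treatment-group survey patients per period. At the assumed 90% and 50%, about 33 (37 × 0.9 = 33.3) count before and about 18 or 19 (37 × 0.5 = 18.5) after.

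**The case against.** The strongest reply has four parts.

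**The information is largely there.** The leftover proportion is listed beside the disposal proportion, and leftover × (1 − disposal) gives the share still holding opioids. In the second row of the table, 0.9 × (1 − 0.289) = 0.64 and 0.5 × 0.8 = 0.40. This stands for a crude figure. But the plan does not say it will be reported, and two separately adjusted difference-in-differences estimates do not combine into an adjusted estimate with an interval.

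**The change in the denominator is not documented.** This also stands. The documents expect doses prescribed and doses taken both to fall, and they give no leftover rate and no new default. If the two fell together, or the new default still exceeded most patients' use, the proportion with any leftovers could barely move and the shift would be small.

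**A change in the conditional proportion may be real.** Patients left with fewer doses may dispose of them differently, and that would be an effect of the intervention. This stands, but the conditional outcome cannot separate such an effect from a change in who is counted.

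**Little rests on this outcome.** It is one of 18 additional secondary outcomes, and the plan states no disposal hypothesis. This limits the weight of the point but does not remove it.

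A reader might also infer that a flat result would mislead. The first row of the table shows otherwise: where tendencies are equal and constant, a flat result correctly reports that disposal did not change, and the fall in leftovers appears in the neighbouring outcome.

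**Conclusion.** The point holds as a minor one. The disposal outcome is conditioned on a day-14 result that the lower default is likely to change in the treatment group only, and the planned model does not deal with that. With individual behaviour fixed, the estimate moved by 8.9 points in either direction when leftovers fell from 90% to 50% and tendencies differed by 20 points. It moved by 4.4 points when leftovers fell from 90% to 70%. All these rates are assumptions; neither size nor direction can be known from the documents.

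Two stronger conclusions might be drawn and are not supported. One is that the treated post-period group with leftovers is known to be smaller and different: that is plausible, but it depends on a default not yet chosen and on unreported consumption. The other is that the plan would hide a real reduction in opioids left in patients' hands: the listed leftover outcome would show much of it. What is missing is a direct, adjusted estimate with an interval for patients still holding undisposed doses, and a caution on reading the conditional contrast. The primary analysis is unaffected.

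**What to change.** In section 10, add one secondary outcome over all patients in the secondary analysis: the proportion with leftover opioid doses not disposed of by day 14, with patients who have no leftovers coded 0. State how partial disposal is coded, and analyse the outcome with the planned difference-in-differences model.

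Keep the among-leftovers proportion. Add a sentence that its between-period contrast is not to be read as a causal effect on disposal, because the intervention may change who is in the denominator.

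The cost is a few sentences. Leftover and disposal status are already needed from the day-14 survey for listed outcomes, so no new data are required. The downside is one more secondary outcome in a long list. It also mixes how many patients have leftovers with what they do with them, so it does not by itself show whether disposal behaviour changed. That is the reason to report both.
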